**Table 1** **Summary of IV doses used in Study COR-001-01 with SC doses that represent corresponding exposure**

COR-001-01 Dose	IV Dosing			SC Dosing		
	q2w (mg)	q4w a (mg)	Cumulative Dose b (mg)	q4w c (mg)	Cumulative Dose c (mg)	Monthly Dose d (mg)
2 mg q2w x12	2	4	24	5.8	34.6	5.8
6 mg q2w x12	6	12	72	17.3	103.9	17.3
20 mg q2w x12	20	40	240	57.7	346.3	57.7

Abbreviations: IV, intravenous; SC, subcutaneous; q2w, every 2 weeks; q4w, every 4 weeks.

a Cumulative dose administered every 4 weeks, i.e., the total of 2 q2w doses given within a 4 week period.

b Cumulative dose over the duration of the study, i.e., the total of 12 q2w doses given during the study.

c Corresponding SC dose, assuming bioavailability (F) of 69.3%.

d Monthly SC dose for 6 monthly doses that corresponds to the SC cumulative dose, i.e., SC cumulative dose divided by 6.

### 3.5.4.3 Exposure for proposed doses relative to IL-6 binding

In the planned study, median trough serum Ziltivekimab concentrations for the 6th dose of 723, 1446, and 2892 ng/mL are expected to be attained with the proposed 7.5, 15, and 30 mg q4w doses, respectively. Those concentrations are sufficient to ensure >99% of plasma IL-6 would be bound (i.e., <1% free IL-6). It is reasonable to expect that this magnitude of IL-6 binding would be associated with perturbation of inflammatory processes.

### 3.5.4.4 Exposures for proposed doses relative to the exposures at NOAEL dose in the toxicology study

COR-001-02 will utilize SC doses of 7.5, 15, and 30 mg administered q4w for a total of 6 months. Based on the clinical PK for Ziltivekimab described above, exposures for the planned doses were estimated. Those exposures were then compared to those attained in a 26-week Good Laboratory Practice (GLP)-compliant toxicology study in cynomolgus monkeys (Study 20134998) to determine the safety factors for the planned clinical study doses.

For these planned doses, safety factors relative to the exposures at the NOAEL SC dose in the 26-week monkey study are at least 76-fold for the Cmax after the 6th dose, and at least 118-fold for the cumulative AUC0-∞ for the 6 doses.

### 3.5.4.5 Exposures for proposed doses relative to the exposures associated with clinically meaningful PD changes in prior clinical studies

In the prior clinical studies, hs-CRP has been found to be a sensitive response to Ziltivekimab exposure, with clinically meaningful decreases even at the lowest doses tested. Decreases were attained soon after the first dose, and the decreases were more prolonged as the Ziltivekimab dose is increased. Therefore, it is reasonable to expect that clinically

meaningful hs-CRP reduction can be attained with the proposed SC 7.5, 15, and 30 mg q4w x 6 regimens.

### **3.6 Safety Plan and Monitoring**

Please see the [Guidance to Investigators section](#) of the IB for a description of safety findings from other IL-6 monoclonal antibodies and guidance for clinical monitoring.

### **3.7 Benefit and Risk Assessment**

Despite the fact that the concept of inflammatory risk in renal patients has been in the public domain for decades, with an active basic research and clinical investigational community focused on its remediation, no therapy has been specifically designed or developed to address it. The advancement of an anti-inflammatory therapy for CKD patients should offer the benefit of myocardial protection and potential treatment of heart failure in this otherwise vulnerable population.

As for the risks associated with administration of Ziltivekimab, nonclinical toxicology studies established the NOAEL by the maximal dose administered (see the Ziltivekimab IB). Both in terms of local and systemic effects, Ziltivekimab was well tolerated, with no apparent adverse findings. Of note, the highest Ziltivekimab dose planned for study allows an over 20-fold margin to NOAEL in the non-clinical toxicology program.

Available data for anti-IL6R (tocilizumab) and anti-IL6 (siltuximab) therapies suggest neutralization of IL-6 have acceptable safety and tolerability profiles for the indications studied. Injection-related and life-threatening hypersensitivity reactions are rare with these agents. Anti-inflammatory therapies in general run the risk of inducing immune suppression and promoting the emergence of infections, sometimes serious in nature. Although anti-IL-6 therapies lower neutrophil counts and may induce frank neutropenia, their rates of infectious complications appear to be similar to other immune-modulatory biologic agents when accounting for patient-specific factors ([Sakai 2015](#), [Sanofi 2016](#)). Gastrointestinal perforation has been associated with anti-IL-6 therapy, however data suggests proper exclusion criteria may mitigate these risks ([Tanaka 2014](#)).

On balance then, the Sponsor proposes the potential risks to patients in this study are justifiable and the benefit-to-risk ratio positive. Patients will be consented as to the potential risks and will be required to sign an ICF documenting their understanding of these risks and willingness to participate in the study.

## 4 SELECTION OF STUDY POPULATION AND CRITERIA FOR WITHDRAWAL

### 4.1 Inclusion Criteria

After signing an informed consent form approved by the Investigator's Institutional Review Board (IRB) or Independent Ethics Committee (IEC) to be eligible, potential study patients must meet all of the following criteria:

- 1) Age  $\geq 18$  years at the time of signing of the Informed Consent Form (ICF).
- 2) Stage 3-5 NDD-CKD, i.e. estimated glomerular filtration rate (eGFR)  $>10$  and  $<60$  mL/min/1.73 m^2 using the CKD-EPI Creatinine Equation ([www.kidney.org/content/ckd-epi-creatinine-equation-2009](http://www.kidney.org/content/ckd-epi-creatinine-equation-2009)).
- 3) Serum hs-CRP level  $\geq 2.0$  mg/L measured during the Screening Period. (Note: C-reactive protein may not be commonly measured in patients with CKD. Targeting patients with a history of advanced stage CKD, ASCVD, anemia, metabolic syndrome, diabetic retinopathy and diabetes for screening will help increase the chances of identifying patients with CRP  $\geq 2.0$ )
- 4) The patient agrees to comply with the contraception and reproduction restrictions of the study ([Appendix G](#)):
  - a) Women of childbearing potential must be using a method of contraception, that is "highly effective" (i.e.,  $<1\%$  failure rate) for at least 3 months following the last dose of study drug;
  - b) Postmenopausal women must have had no menstrual bleeding for at least 1 year before initial dosing and either be over the age of 60-years or have an elevated plasma follicle-stimulating hormone (FSH) level (i.e.,  $>40$  mIU/mL) at Screening;
  - c) Women of childbearing potential must have a documented negative pregnancy test result at Screening. Patients with elevated  $\beta$ -HCG levels believed to be due to end-stage renal disease may be enrolled if documented to not be pregnant;

AND

All male patients, from the day of dosing until the final study visit, unless surgically sterile, must be willing to use a condom with a partner (male patients with partners of childbearing potential must be willing to use 2 effective methods of birth control, 1 should be condom with spermicide) to prevent pregnancy and drug exposure of a partner, and refrain from donating sperm or fathering a child.

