### 3.2 Study Schematic

**Figure 5 Study Flow**

Ziltivekimab Dose Level 1, 2 or 3 (N=180); N=60 in each level															
		Placebo (N=60)													
Visit Number	Screening		Treatment Period											Safety F/U	
	-2	-1	1	2	3	4	5	6	7	8	9	10	11/ET	12	13/ET
Visit Day Window	-14	-7	1	8	22	29-35	43-49	57-63	85-91	113-119	141-147	155-161	162-168	190-196	218-224
Visit Window		±2	1	±2	±2										
Visit Week	-2	-1	1	2	4	5	7	9	13	17	21	23	24/ET	28	32/ET

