### 3.5.4.1 Pharmacokinetic modeling

To date, the Ziltivekimab clinical program is comprised of 2 studies, both of which are placebo-controlled ascending dose studies. In the first of these studies (Study COR-001-01), patients with ESRD were administered intravenous (IV) infusions of study drug every 2 weeks for a total of 6 doses. Ten patients per cohort were randomized in a 1:4 ratio to placebo or Ziltivekimab (2, 6, and 20 mg).

In the second study (Study COR-001-SC1), patients with CKD were administered single subcutaneous (SC) doses of study drug. Four patients per cohort were randomized in a 1:3 ratio to placebo or Ziltivekimab (5, 15, and 50 mg).

The PK parameters are generally consistent with those expected for a monoclonal antibody. Absolute bioavailability (F) of SC administered Ziltivekimab is 69%, and the mean time of occurrence for peak serum Ziltivekimab concentrations ( $t_{max}$ ) after SC dosing ranged from 8 to 15 days, with an absorption half-life of 3 days. Terminal elimination half-lives ( $t_{1/2,z}$ ) differed between the ESRD patients (mean  $t_{1/2,z}$  ranging from 38 to 44 days) and CKD patients (mean  $t_{1/2,z}$  ranging from 48 to 56 days). While these results suggest that the rate of Ziltivekimab elimination may increase with decreasing renal function, a prior observation in rheumatoid arthritis patients that Ziltivekimab clearance is much slower than the glomerular filtration rate implies that the apparent elimination rate difference is not due to renal function *per se*, but more likely other physiological changes that accompany decreased renal function.

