#### **4.3 Criteria for Discontinuation of Study Drug**

It may be necessary for a participant to permanently discontinue study intervention. If study intervention is permanently discontinued, the participant shall remain in the study to be evaluated on all early termination and safety follow-up procedures per the Schedule of Assessments (SOA) in [Section 5.3.9](#) and [Section 5.6](#). Study drug may be prematurely discontinued for a number of reasons, including:

- An intercurrent illness at the discretion of the investigator;
- Any intolerable AE that cannot be ameliorated by appropriate medical intervention or that in the opinion of the Medical Monitor or Investigator would lead to undue risk if the patient were to continue on treatment;
- In the event of severe injection related reactions, anaphylaxis, or hypersensitivity ([Section 8.2](#) and [Section 4.5](#));
- If at any point during the study,  $\geq 10\%$  of subjects enrolled experience anaphylaxis, additional enrollment will stop in the study, and all patients in the study will discontinue receiving study drug ([Section 8.2](#) and [Section 4.4](#));
- Pregnancy;
- Organ transplantation or development of another indication for chronic immunosuppression;

Reasons for all withdrawals/discontinuations of Study Drug will be recorded, and the Medical Monitor should be informed of all such cases as they occur. Temporary discontinuation of study intervention and restarts may be performed per [Section 4.5](#).

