#### **4.6 Participant Discontinuation/Withdrawal from the Study**

The following are descriptions of participant discontinuation and withdrawal from the study. This is not an exhaustive list, and each instance should be evaluated on a case-by-case basis.

- Withdrawal of consent. A participant may elect to withdraw consent to treatment at any time.
- Participants withdrawing their consent for all study procedures must be given the option to continue to give consent for passive follow-up (i.e., by means of chart review) for AEs.
- Participants discontinuing study drug treatment after receiving any amount of study drug should undergo all early termination and safety follow-up study procedures per the SOA ([Section 5.3.9](#) and [Section 5.6](#)) unless the participant also explicitly withdraws consent for these procedures as mentioned above. The study drug has a long pharmacodynamic effect. Therefore, continued monitoring for pharmacodynamic effects and safety is prudent.

- A participant may be withdrawn at any time at the discretion of the investigator for safety, behavioral, compliance, or administrative reasons. Participation in the early termination and safety follow-up procedures will be evaluated on a case-by-case basis. If possible, participants should take part in the early termination and safety follow-up procedures in the SOA ([Section 5.3.9](#) and [Section 5.6](#)).
- If the participant withdraws consent for disclosure of future information, the sponsor may retain and continue to use any data collected before such a withdrawal of consent.
- If a participant withdraws from the study, the participant may request destruction of any samples taken and not tested. The investigator must document this in the site study records.

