### **5.3 Treatment Period (Study Weeks 1 - 21)**

**Important:** Study Visits during which Study Drug injections are required should be planned for the same day of the week so that Study Drug administration can occur on a schedule of every 28 days. See [Section 6.1.1](#) for guidance on missed doses.

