#### Special Situations

Patients who miss a dose of Study Drug may receive the missed Study Drug up to 15 days later.

If the missed dose cannot be administered within this time frame, the dose should be considered “missed” and the next dose administered at the next study visit as planned.

In the above special situations, please ensure that blood testing and PK sampling that is timed with the administered dose must be adhered to.

**Table 3** Planned Ziltivekimab Doses and Administered Volumes

	Dose Cohort 1	Dose Cohort 2	Dose Cohort 3	Dose Cohort 4
Intervention Name	Ziltivekimab	Ziltivekimab	Ziltivekimab	PBO
Type	Active Drug	Active Drug	Active Drug	Comparator
Dose	7.5 mg	15 mg	30 mg	N/A
Dose Administration	7.5 mg in 1 mL injection	15 mg in 1 mL injection	30 mg in 1 mL injection	1 mL PBO injections\
Route of Administration	SC injections	SC injections	SC injections	SC injections
Frequency	Every 28 days per SOA	Every 28 days per SOA	Every 28 days per SOA	Every 28 days per SOA

Abbreviations: PBO = placebo; SC = subcutaneous; SOA = schedule of activities

The date and time of administration of Study Drug must be recorded in the appropriate sections of the CRFs.

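### Men's contraception ends at the final study visit instead of a set time after the last dose: 71 to 83 days after an on-schedule dose 6, shorter than the women's 3-month minimum

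*Protocol*

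**What the plan says.** Inclusion criterion 4 appears in the synopsis and in section 4.1, and its text is largely repeated in Appendix G.

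- **Women of childbearing potential** (synopsis and 4.1): highly effective contraception "for at least 3 months following the last dose of study drug". Appendix G repeats the requirement without the end point.
- **Men** (synopsis, 4.1 and Appendix G): the rule covers "All male patients, from the day of dosing until the final study visit, unless surgically sterile". Its stated aims are to prevent pregnancy and to keep a partner from being exposed to drug. No interval after the last dose is given.

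Several other parts of the protocol decide how long the men's period lasts:

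- Figure 5, in the row "Visit Day Window", puts Visit 9 (Week 21, dose 6) on Days 141-147 and Visit 13 (Week 32, the last visit) on Days 218-224.
- Section 5.3 plans visits so that "Study Drug administration can occur on a schedule of every 28 days".
- Section 6.1.1, Special Situations: "Patients who miss a dose of Study Drug may receive the missed Study Drug up to 15 days later".
- Section 5.6 gives a patient who leaves the study before Week 24 an early termination visit, with no minimum interval since the last dose.
- Section 4.3 says that after permanent discontinuation of drug "the participant shall remain in the study to be evaluated on all early termination and safety follow-up procedures".

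On persistence of the drug, section 3.5.4.1 gives a mean terminal half-life in CKD patients "ranging from 48 to 56 days", and section 4.6 states: "The study drug has a long pharmacodynamic effect".

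**The concern.** The rule for men protects against conception and partner exposure while drug is in the body, so its natural reference point is the last dose. The protocol uses a calendar event instead. The length of protection then depends on when dose 6 was given, where the last visit falls in its window, and whether the man stays in the study. It moves the wrong way in the cases that matter: a late dose can shorten it, and so does early withdrawal. Even when everything runs to plan, men are released before women are, with no reason given.

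A man who follows the criterion exactly could therefore stop contraception sooner after his last dose than the protocol accepts for women.

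**Working it through.** The protocol states no figure for the men's interval, so there is none to reproduce. It follows from the visit windows.

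**Inputs.** Dose 6 on Day 141-147 and final visit on Day 218-224 (Figure 5). Late-dose allowance 15 days (6.1.1). Half-life 48-56 days in CKD and 38-44 days in ESRD (3.5.4.1). Projected dose-6 troughs 723, 1446 and 2892 ng/mL for 7.5, 15 and 30 mg (3.5.4.3). Assumption: 3 months = 90 days.

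**Step 1: men's interval on schedule** (final visit day minus dose 6 day).
- Shortest: 218 − 147 = 71 days
- Longest: 224 − 141 = 83 days
- Nominal: dose 6 on Day 1 + 5 × 28 = 141; 218 − 141 = 77 days

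Shortfall against 90 days: 90 − 83 = 7 to 90 − 71 = 19 days; nominal 90 − 77 = 13 days.

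**Step 2: half-lives elapsed** (days ÷ half-life).

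| Interval | CKD, 48-56 days | ESRD, 38-44 days |
|---|---|---|
| Men, 71-83 days | 71/56 = 1.27 to 83/48 = 1.73 | 71/44 = 1.61 to 83/38 = 2.18 |
| Women, 90 days | 90/56 = 1.61 to 90/48 = 1.88 | 90/44 = 2.05 to 90/38 = 2.37 |

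**Step 3: dose 6 given late.** If it is given 15 days after the window closes, dosing is on Day 147 + 15 = 162. If Visit 13 keeps its window, the shortest interval is 218 − 162 = 56 days, or 56/56 = 1.0 to 56/48 = 1.17 half-lives in CKD patients.

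**Step 4: early withdrawal.** For a man who withdraws before Week 24, the early termination visit can be his final visit. Section 5.6 sets no minimum time since the last dose, so his obligation can end soon after a dose. A man who only stops drug stays in follow-up under 4.3 and 4.6 and is not affected.

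**Step 5: the women's 3 months against the protocol's PK (secondary).** Decline from the day-28 trough after dose 6, level = trough × 0.5^((t − 28)/half-life). For 30 mg at t = 90:
- half-life 48: 2892 × 0.5^(62/48) = 1181 ng/mL
- half-life 56: 2892 × 0.5^(62/56) = 1343 ng/mL

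Both exceed 723 ng/mL, the lowest of three troughs that section 3.5.4.3 says bind more than 99% of IL-6. This assumes mono-exponential decline.

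**The case against.** **The men's end point is in effect tied to dosing.** The synopsis and section 3.4 start safety follow-up 4 weeks after dose 6 and run it for 8 weeks, so the intended interval is close to 12 weeks (84 days). The 71-day figure needs dose 6 on the last day of its window and the final visit on the first. This stands in part: 77 days is the fairer planning figure. But 84 days is still under 90, and the tie is to a scheduled dose 6, not to the last dose received.

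**The late-dose case is one reading.** The protocol does not say whether Week 32 moves with a late dose 6. That is true, and the 56 days depend on Visit 13 keeping its window. The protocol should not leave this open.

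**A reader might infer that 3 months is too short, and that 140 days (the upper end of when the 30 mg arm is projected to reach 723 ng/mL: 28 + 2 × 56) or five half-lives (240-280 days) is required.** The protocol does not support this. It sets no washout criterion. The 723 ng/mL figure is only the 7.5 mg dose's projected trough, neither a point where binding is said to fall off nor a reproductive-risk threshold. The 48-56 day half-life comes from a small study in patients with eGFR 20-60 (1.4.2, 3.5.4.1), while this trial admits eGFR above 10, and at the ESRD half-life 90 days exceeds two half-lives. The Investigator's Brochure is not shown, and the guidance named in Appendix G is redacted.

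**A reader might also take Appendix G as releasing women earlier.** It does not: it is silent, and 4.1 states the women's duration.

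**Pregnancies are followed anyway.** Section 9.8 requires reporting for patients and for male patients' partners with no stated cut-off. That detects pregnancies; it does not prevent them.

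**Conclusion.** The point holds for the men's rule. It is not fixed to the last dose. On schedule it runs 71 to 83 days after dose 6 (77 nominal), or 1.3 to 1.7 half-lives in CKD patients, and falls 7 to 19 days short of the women's minimum. It can drop to 56 days with a late dose 6 and an unmoved last visit, and to much less for a man who withdraws. The day counts rest only on the protocol's windows and on 3 months being 90 days. The half-life counts rest also on the CKD range applying to those enrolled, which is less certain at eGFR below 20.

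The adequacy of 3 months is a question for the sponsor, not an error shown by the protocol. Ninety days is 1.6 to 1.9 half-lives in CKD patients and 2.05 to 2.37 at the ESRD half-life, and the 30 mg arm is projected to hold 1181 to 1343 ng/mL then. That is reason to check the figure, but the protocol supports no specific longer period.

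**What to change.** 1. In the synopsis, section 4.1 and Appendix G, define the men's period as a fixed time after the last dose actually received, no shorter than the women's (at least 3 months). State that it applies to men who stop drug and to men who leave the study early.
2. Repeat the women's end point in Appendix G.
3. Have the sponsor check the 3-month figure for both sexes against its PK and reproductive-toxicity data, and cite the basis.

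The cost is amendment wording and a consent-form update. On schedule, men use contraception for about 1 to 3 more weeks, and early leavers for longer. This runs past the last visit, so nobody would check it unless a contact such as a phone call is added. Treatment, visits and analysis are unchanged.

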### 4.2 Exclusion Criteria

Participants are excluded from the study if any of the following criteria apply:

### **Laboratory Values**

1. Absolute neutrophil count  $<2.0 \times 10^9/L$  during screening.
2. Platelet count  $<120 \times 10^9/L$  during screening.
3. Spot urine protein to creatinine ratio  $>4000 \text{ mg/g}$ , or  $4.0 \text{ g/g}$ .
4. Alanine aminotransferase (ALT) or aspartate aminotransferase (AST)  $>2.5 \times \text{ULN}$  during screening.
5. Positive testing for tuberculosis (TB) during screening. Blood testing (e.g., QuantiFERON) is preferred but a purified protein derivative (PPD) skin test read within 48-72 hours by a qualified healthcare professional may also be performed. If a patient is PPD positive but QuantiFERON negative the patient is eligible.
6. Evidence of human immunodeficiency virus-1 (HIV-1) or HIV-2 infection by serology measured during screening.
7. Hepatitis B or C by serology (e.g. hepatitis B surface antigen or hepatitis C antibody positive) measured during screening.

### **Medical Conditions or Diseases**

8. Expected to require blood transfusion within 12-weeks post-randomization.
9. Thromboembolic event within 12-weeks prior to randomization.
10. Clinical evidence or suspicion of active infection.
11. History of peptic ulcer disease or gastrointestinal ulceration in the 12-months prior to randomization.
12. History of active diverticulitis in the 12-months prior to randomization.
13. History of inflammatory bowel disease that has been clinically active during the 12-months prior to randomization.
14. Uncontrolled hypertension (defined as an average SBP  $>160 \text{ mmHg}$  or an average diastolic blood pressure (DBP)  $>100 \text{ mmHg}$  during screening. Patients may be re-evaluated within 2 weeks, at the discretion of the investigator for this criterion if anti-hypertensive therapy has been started or increased as a result of initial screening blood pressure being above these limits.
15. Planned coronary revascularization (PCI or CABG) or any other major surgical procedure.

16. Major cardiac surgical, non-cardiac surgical or major endoscopic procedure within the past 6 months prior to Randomization.
17. History of New York Heart Association Class IV congestive heart failure within 12-weeks prior to randomization.
18. Actively treated or active malignancy during the 1-year prior to randomization with the exception of successfully treated nonmetastatic basal cell or squamous cell carcinomas of the skin and/or local carcinoma in situ of the cervix.
19. History of bone marrow or solid organ transplant or anticipated to receive an organ transplant during the time frame of the study.
20. Known allergy to the study drug or any of its ingredients.

